As per recent clinical guidelines (2), all patients at entry will receive dietary advice by study coordinator, diabetes educator, or registered dietician specifically geared towards type 2 diabetes patients. They will be advised to adhere to 150 minutes of weekly aerobic exercise (50-70% of maximal heart rate). Patient's activity will be monitored using accelerometers and will be downloaded at visit 2 and visit 3 by the study staff.

Subjects will be taking 5.0 mg of Linagliptin or placebo. Dose titration of insulin will be allowed so that the HbA1C is maintained below 10%.

Visits with outcome measurements will be scheduled for the morning while overnight fasting (except water) to reduce diurnal variability, and clinical parameters will be obtained at scheduled office visits as depicted in the study schema and will be measured at each outcome visit as follows:

Week -4: Subjects will be screened and eligibility will be verified based on physical and laboratory tests. Equal numbers of male and female patients will be recruited. All patients will be educated on the recommended lifestyle changes of maintaining a level of aerobic activity of 150 minutes/ week (non-supervised) and adherence to a healthy diet as advised by the study coordinator, a diabetes educator, or a dietitian as part of the type 2 diabetes patient management plan [2]. We will allow 4 weeks for the patients to reach a steady state while implementing diet and exercise changes.

Week 0: At this stage patients will be randomized into the study. Subjects will have the first set of measurements. We will make sure that patients still meet the inclusion criteria. They will be started on medication or placebo and will be encouraged to continue 150 minutes/week of moderate physical exercise and dietary management for the remainder of the study.

Weeks 0, 6 and 12: Subjects will all have the same measurements and will continue on study medication or placebo. All primary and secondary measures as outlined before will be carried out.

The cellular outcome measures are as follows:

From MNC population (pre magnetic column sorting):

A. FACS Analysis, 1 million cells in each tube/assay column. 12 tubes-- total 12 million. (All labelling antibodies are obtained from Miltenyi Biotec except Sytox blue-Invitrogen and anti-VEGFR2/KDR-R&D systems)

1. Unlabelled

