5 STATISTICAL CONSIDERATIONS

Statistical Analysis:

Sample Size Estimation:

The total sample size requested, accounting for attrition over the 12-week period, is 20 subjects per group or 40 subjects total. We plan to allow for 25% attrition (drop out), therefore plan to screen 55 patients over three years.

Sample size estimates were based on the effects of exercise on CD34+/KDR+ cells and VEGF, as described in the literature (47-50).

This is a pilot study and accurate power calculation is not feasible.

The effect of a single session, as well as extended training, on healthy subjects or those with existing cardiovascular conditions appears to increase the CD34+/KDR+ cells and VEGF.

To compute sample size we used the approach suggested by Diggle, Liang, & Zeger (1994)(51) which compares the rates of change in the two study groups over time. This approach incorporates the number and interval of time points and the correlation among repeated measures. For this study, we will employ one baseline and two follow-up measures at 6 and 12 weeks. Further, we will assume a correlation 0.60 among repeated measures of the outcome. We consider this a conservative estimate since Frison and Pocock (1992) (52) suggest a correlation of 0.65 as reasonable in the absence of an existing estimate. We also note that as this correlation increases, statistical power also increases.

The results in the table below show the expected mean difference in study groups at the end of follow-up, as well as the average rate of change in the two groups at 80% power and 90% power. To estimate the effect of Linagliptin on the CD34+/KDR+ cells, we expect that the effect would be at least 25% greater than the effect seen for exercise alone. Using the results from Sandri et al. (2005)⁴⁹ for the rate of change and the variability, the CD34+/KDR+ cells increased an average rate of about 4/wk with a standard deviation of about 15. Thus, for a 25% increase in the rate of change for the CD34+/KDR+ cells due to Linagliptin, a sample size of 18 subjects per group would provide about 84% power, assuming measures taken at baseline and 2 equally-spaced time points over 12 weeks. At the conclusion of follow-up, we would expect study groups to differ by an average of 12 cells. If the effect of Linagliptin is only 20%, a sample of 18 would provide about 70% power, whereas a sample of 20 would provide about 73% power.

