For VEGF, the results from Sandri et al. (2005)(49) were mixed with one study group showing a .6 pg/mL per week increase and another showing a 0.5 pg/mL per week decrease after 4 weeks of training. If we assume that Linagliptin will increase VEGF consistently at 0.3 pg/mL per week difference in slopes compared with exercise alone, then assuming a standard deviation of 5 and correlation or 0.60 among repeated measures, a sample size of 18 per group would provide about 77% power to detect a difference in slopes of 0.3 pg/mL per week or a mean difference in the groups at the end of the study of 3.6 pg/mL. A sample size of 27 would provide about 90% power to detect the same effects.

Thus, we feel that a sample size of at least 18 subjects per group with complete data would provide sufficient power for the study outcomes. In order to insure that we will have 18 per group who complete the study, we will enroll 20 subjects per group in order to account for attrition over the 12-week intervention period.

Biochemical Measure	Mean difference at end of 12 weeks	Sample Size per group	Power
CD34+/KDR+	12 cells	18	0.84

cells	(25% increase; 4/wk vs. 5/wk)	22	0.90
VEGF, pg/mL	3.6 pg/mL (50% increase; (0.6/wk vs. 0.9/wk)	18	0.77
		27	0.90

Sub-Group Subject Number Breakdown:

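### The 84% power is power for a 12-cell difference at week 12; equating that with a 25% gain over exercise assumes, without justification, that the exercise slope runs on for 12 weeks after the lifestyle run-in

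*Combined protocol and SAP*

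**What the plan says.** Section 5 (Sample Size Estimation) takes its control-arm figures from a published exercise study in which "the CD34+/KDR+ cells increased an average rate of about 4/wk with a standard deviation of about 15". It expects linagliptin to do better: "we expect that the effect would be at least 25% greater than the effect seen for exercise alone". The sample size table shows how this was implemented: "25% increase; 4/wk vs. 5/wk". From this the plan concludes that "we would expect study groups to differ by an average of 12 cells" at the end of follow-up and that "a sample size of 18 subjects per group would provide about 84% power". The method compares rates of change over visits at weeks 0, 6 and 12, and "we will assume a correlation 0.60 among repeated measures of the outcome". Section 5 then concludes that 18 completers per group is enough for the study outcomes.

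The significance level is 0.05 (Synopsis; Section 5, Sub-Group Subject Number Breakdown). Neither place says whether the test is one- or two-sided.

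Two other statements bear on the slope. Section 4.5 starts diet and exercise in all patients at week -4, before the week 0 baseline: "We will allow 4 weeks for the patients to reach a steady state while implementing diet and exercise changes". In the VEGF paragraph of Section 5, the same exercise study is described as having one group with a rise and "another showing a 0.5 pg/mL per week decrease after 4 weeks of training".

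**The concern.** A slope of 4 cells per week held for 12 weeks means controls gain 4 × 12 = 48 cells after baseline and treated patients 5 × 12 = 60. The only reason given for the 12-cell difference is that it is a quarter of that 48-cell gain. But both arms have already exercised for 4 weeks when the baseline sample is taken, and those weeks are meant to bring patients to a steady state. The plan does not say why the exercise gain should then run on undiminished for another 12 weeks. If it does not, a 25% advantage over exercise is fewer than 12 cells, and the stated power does not apply to it.

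The stake is interpretation. A reader of a null result would take it that the trial had 84% power against a 25% improvement over exercise. That is true only if the extrapolation holds and only on the unstated basis that gives 84%.

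**Working it through.** **Inputs (Section 5 unless noted).** SD 15; correlation 0.60; visits at weeks 0, 6 and 12; 18 per group, equal allocation; slope difference 5 − 4 = 1 cell per week; alpha 0.05, sidedness not stated.

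**Step 1: reproduce the stated power.** For the slope comparison the plan names, with Σ(t − t̄)² = 36 + 0 + 36 = 72:

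- SE of the slope difference = √[2 × SD² × (1 − ρ) / (n × 72)] = √[2 × 225 × 0.40 / (18 × 72)] = √(180/1296) = 0.373.
- z = 1/0.373 = 2.68.
- One-sided power = Φ(2.68 − 1.645) = 85.0%.
- Two-sided power = Φ(2.68 − 1.960) = 76.5%.

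With a t reference the figures are 83.8% and 74.1%. So 84% reproduces one-sided and not two-sided. The other powers in Section 5 behave the same way:

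| Outcome, slope difference | n per group | Stated | One-sided | Two-sided |
|---|---|---|---|---|
| CD34+/KDR+, 1.0 per week | 18 | 84% | 85.0% | 76.5% |
| CD34+/KDR+, 1.0 per week | 22 | 90% | 90.7% | 84.3% |
| CD34+/KDR+, 0.8 per week | 18 | 70% | 69.2% | 57.4% |
| CD34+/KDR+, 0.8 per week | 20 | 73% | 73.2% | 61.9% |
| VEGF, 0.3 per week (SD 5) | 18 | 77% | 77.9% | 67.5% |
| VEGF, 0.3 per week (SD 5) | 27 | 90% | 90.5% | 84.1% |

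A two-sided baseline-adjusted comparison at week 12 also comes close to 84%: SD 15 × √(1 − 0.36) = 12, SE 12 × √(2/18) = 4.0, power Φ(3.00 − 1.96) = 85.1%. It is not the method the plan names.

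**Step 2: express it in cells.** With three equally spaced visits, the slope comparison is equivalent to comparing change from week 0 to week 12. The variance of a change is 2 × 225 × 0.40 = 180, so the SE of the difference at n = 18 is √(2 × 180/18) = 4.47 cells, and 12/4.47 = 2.68 as before. The control slope does not enter; only the difference does.

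**Step 3: vary how long the 4-per-week rise lasts.** The documents do not give the training length behind the cell figure. The 4-week duration is stated for VEGF from the same source, so it is used here as one end of a range. The other end is the 12 weeks the plan implies. The difference is 0.25 × 4 × weeks, with n = 18:

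| Weeks of rise | Exercise gain | 25% of it | Difference/SE | Two-sided | One-sided |
|---|---|---|---|---|---|
| 4 | 16 cells | 4 cells | 0.89 | 14% | 23% |
| 6 | 24 cells | 6 cells | 1.34 | 27% | 38% |
| 8 | 32 cells | 8 cells | 1.79 | 43% | 56% |
| 12 | 48 cells | 12 cells | 2.68 | 77% | 85% |

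**The case against.** Four points on the other side carry weight.

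- **The label agrees with the plan's own definition.** The plan defines the effect as a 25% increase in the weekly rate. Five against four is exactly that, and 1 × 12 = 12. A reader might infer an arithmetic slip; there is none. What is missing is a reason for carrying the rate to week 12.
- **A flat control slope would not by itself change the power.** If controls stayed level and the drug added 1 cell per week, the difference would still be 12 cells. This stands. The extrapolation matters because it is the only support offered for 1 cell per week.
- **The plateau and the 16-cell gain are inferences.** The steady-state sentence is about adopting diet and exercise and does not mention cell counts. Exercise continues after week 0, with 16 weeks of lifestyle change in all (Section 3.1). The investigators' preliminary exercise study (Section 1) reports early improvement in gene expression and function, which is neither a plateau nor a count. The 4-week duration is attached to VEGF only, and the reference list describes the source as three randomized studies, so the cell figure may come from a different one. A reader might conclude that 12 cells is 75% of the observed exercise effect (12/16); the documents do not establish that.
- **The plan is candid about its limits.** It calls itself a pilot that cannot be powered accurately, gives a 20% scenario, and quotes 73% in the Synopsis. But the 20% scenario uses the same 12-week extrapolation (0.8 × 12 = 9.6 cells), and Section 5 still concludes that 18 per group is enough. The caveat does not tell the reader what that conclusion depends on.

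**Conclusion.** The concern holds in a limited form. The 84% is power for a 12-cell difference at week 12 with SD 15, correlation 0.60 and 18 per group. It is power for a 25% gain over exercise only if the exercise slope of 4 cells per week continues through weeks 0 to 12. The plan neither states nor defends that condition, and its own run-in makes it doubtful. On the named method the figure also needs a one-sided test; two-sided it is about 77%.

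If the rise lasted only 4 weeks, power for a 25% effect falls from 77% to 14% two-sided, or from 85% to 23% one-sided. Power is low on either basis, but the 4-week duration is an assumption.

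A reader might set roughly 15% against the stated 84%. That is not a fair contrast: a figure near 15% is two-sided, whereas 84% reproduces under the named method only one-sided, so part of the apparent fall is a change of basis. Nor do the documents show that the sponsor intended a one-sided test. They show only that sidedness is unstated and that the stated figures match that basis under the named method.

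**What to change.** In Section 5 (Sample Size Estimation and its table):

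1. Present 12 cells at week 12 as the difference the design targets.
2. State that reading this as a 25% gain over exercise assumes the exercise slope of 4 cells per week continues for 12 weeks after the run-in. Give the reason for that assumption, or say that there is none.
3. State whether the test is one- or two-sided and restate all the powers on that single basis. If two-sided under the named method, the main figure becomes about 77%.
4. Show power over differences of 4 to 12 cells, as in the second table above.
5. Limit the sentence on adequate power to differences of about 12 cells.

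The text should not present 12 cells as 75% of a 4-week exercise effect, or power of about 15%, as established figures; both rest on a duration the documents do not give for cell counts.

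The cost is wording. Enrolment, visits and analysis are unchanged, though the stated power becomes less favourable if the test is two-sided.

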
Criteria for Evaluation: (Efficacy, safety, stopping rules, etc.)
	
Subjects will be screened at week -4, then evaluated for end points at weeks 0, 6 and 12. Follow up phone call will be done 30 days after last dose of study drug to assess for adverse effects.
 
Study participation will be stopped for adverse effects at the discretion of the study investigator. Subjects may stop study participation at any time and for any reason.

Statistics:
	
The total sample size is requested, after accounting for attrition over the 12-week period, is 20 subjects per group or 40 subjects total. Sample size estimates were based on the effects of exercise on CD34+/KDR+ cells as described in the literature. The effect of a single session, as well as extended training, on healthy subjects or those with existing cardiovascular conditions appears to increase the CD34+/KDR+ cells.
 
This is a pilot study as a result appropriate power calculation is not feasible. We however did conduct power analysis, which provided us with 73% power (see statistics section). A p-value of less than 0.05 will be considered statistically significant.

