To estimate the effect of linagliptin on CD34+/KDR+ cells, we originally proposed a sample size of 20 per group in 2 groups, giving us power = .73, assuming alpha=.05, between time points of .60 and equal allocation between groups. Thus, the group x time interaction effect size we were modeling was an interaction that explained 3% of total variance, or a partial eta-square = .0291. Using 3 groups (Insulin only, metformin only, metformin + insulin), with the same effect size, we would achieve this same level of power using a total sample size of 51 (17 per group). However, given the relatively small numbers of potential participants with insulin-only (n=21) and insulin+metformin (n=54), and the relative large number with Metformin only (260), we will need to change the allocation ratio between groups. Maintaining the same total sample size as originally proposed (40), we will allocate patients from each group in the following numbers: **Metformin only (22), Metformin+insulin (12), Insulin only (6)**. We recognize that we will be underpowered for comparisons between the Metformin + insulin versus Insulin groups. However, comparisons with the Metformin-only group will still have reasonable power. Given the small number of potential patients with Insulin-only, this is a feasible strategy for including this group in the analysis.

Data Analysis.

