The distributional assumptions of all measures will be examined. Means and standard deviations will be computed for continuous measures and proportions for categorical variables. Graphical representations of the mean group slopes and individual slopes will be generated and inspected. Study groups will be compared to determine whether any imbalance between the groups on patient characteristics remain after randomization. If imbalance is evident, by inspection, all models will be adjusted for the unbalanced covariates. Change in outcome over time will be examined using a multilevel approach with linear mixed models (LMM) (53, 54). The longitudinal multilevel modeling approach will enable us to examine characteristics of within-person change, as well as between-group differences that may influence change. LMMs handle missing data more efficiently than traditional ANOVA designs. In the linear mixed models, the patient is considered a random effect and the outcome measured at specific time points is nested within patient. In an initial model containing only the variable TIME, we will use a likelihood ratio test to determine whether a random effect for time should be modeled.

The model below represents a random intercept for patient and a random coefficient for TIME.

$$Y_{ij} = \beta_0 + \beta_1 Time_{ij} + u_{i0} + u_{i1} Time_{ij} + \varepsilon_{ij}$$

We will examine whether TIME may be modeled linearly by testing the added contribution of TIME (represented with two indicator variables) to a model with TIME as a single continuous variable. Assuming time may be modeled as a continuous variable, subsequent analyses will add study group and other patient characteristics as covariates. We are particularly interested in whether there is a significant interaction between study group and time, adjusting for other patient level covariates. A significant interaction would indicate that the slopes in outcome over time differ by study group. If the global test of interaction is significant, subsequent significance testing of the pairwise comparisons of group slopes group will be adjusted for multiple comparisons. The model also includes coefficients for the group-by-time interactions and random effects for patient and time.

$$Y_{ij} = \beta_0 + \beta_1 Time_{ij} + \beta_2 Group_i + \beta_3 (Time_{ij} \times Group_i) + u_{i0} + u_{i1} Time_{ij} + \varepsilon_{ij}$$

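### The six stated powers fit a one-sided 5% test, but the planned test asks whether slopes differ at p<0.05; two-sided, 73% becomes about 62% and 84% about 76.5%

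*Combined protocol and SAP*

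**What the plan says.** Section 5 (Sample Size Estimation) bases power on a method "which compares the rates of change in the two study groups over time". It assumes three visits (weeks 0, 6 and 12) and a correlation of 0.60 among repeated measures. For CD34+/KDR+ cells it takes a rate of 4 per week with exercise alone, a standard deviation of 15, and a linagliptin effect of 25% or 20% on that rate.

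- 25% effect: "a sample size of 18 subjects per group would provide about 84% power". The table adds 90% at 22 per group.
- 20% effect: "a sample of 18 would provide about 70% power, whereas a sample of 20 would provide about 73% power".
- VEGF (standard deviation 5, slope difference 0.3 pg/mL per week): "a sample size of 18 per group would provide about 77% power", with 90% at 27 per group.

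The section then concludes that 18 completers per group are enough and enrols 20. The Synopsis (Statistics) refers to a power analysis "which provided us with 73% power (see statistics section") and sets the threshold: "A p-value of less than 0.05 will be considered statistically significant". The Sub-Group Subject Number Breakdown repeats the .73, "assuming alpha=.05, between time points of .60 and equal allocation between groups". For the analysis itself, Data Analysis says: "A significant interaction would indicate that the slopes in outcome over time differ by study group".

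None of these places says whether the 0.05 is one-sided or two-sided.

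**The concern.** The planned test is a group-by-time interaction in a linear mixed model, judged at p<0.05. As described it has no direction: a slope difference either way counts. The sub-group paragraph also expresses the same .73 as a partial eta-square, which has no direction either. Power for such a test should use the two-sided 5% critical value (1.960), but the published figures fit the one-sided value (1.645).

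These powers are the stated justification for the trial's size, and 73% is the only power figure in the Synopsis. If they are too high, the plan claims a chance of detecting its target effects that its own test does not have. A non-significant result could then be given more weight as evidence against an effect than it deserves.

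**Working it through.** **Inputs (Section 5, Sample Size Estimation).** Visit times 0, 6, 12 weeks; correlation ρ = 0.60; SD = 15 (CD34+/KDR+) or 5 (VEGF). Slope differences d: 25% of 4 = 1.0 per week; 20% of 4 = 0.8 per week; VEGF 0.3 per week. Alpha is 0.05 (Synopsis and sub-group paragraph), sidedness not given.

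**Formula.** With mean visit time 6, S = (0−6)² + (6−6)² + (12−6)² = 72. The standard error of the slope difference with n completers per group is

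SE = √[2·SD²·(1−ρ) / (n·S)], z = d/SE.

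Power (normal approximation) is Φ(z − 1.645) one-sided and Φ(z − 1.960) two-sided.

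**Worked case, 25% effect, n = 18.** 2 × 225 × 0.40 = 180; n·S = 18 × 72 = 1296; SE = √(180/1296) = 0.3727; z = 1.0/0.3727 = 2.683.

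- One-sided: Φ(1.038) = 0.850, against 84% stated.
- Two-sided: Φ(0.723) = 0.765.

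**Headline case, 20% effect, n = 20.** SE = √(180/1440) = 0.3536; z = 0.8/0.3536 = 2.263.

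- One-sided: Φ(0.618) = 0.732, against 73% stated.
- Two-sided: Φ(0.303) = 0.619.

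**All six figures.** The last column is the number per group at which a two-sided test reaches the stated power: n = 2(1.960 + z_power)²·SD²·(1−ρ)/(72·d²), rounded up.

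| Case | n per group | Stated | One-sided 5% | Two-sided 5% | Two-sided, t critical values | n for stated power, two-sided |
|---|---|---|---|---|---|---|
| CD34+/KDR+, 25% | 18 | 84% | 85.0% | 76.5% | 74.1% | 22 |
| CD34+/KDR+, 25% | 22 | 90% | 90.7% | 84.3% | 82.6% | 27 |
| CD34+/KDR+, 20% | 18 | 70% | 69.2% | 57.4% | 55.0% | 25 |
| CD34+/KDR+, 20% | 20 | 73% | 73.2% | 61.9% | 59.7% | 26 |
| VEGF | 18 | 77% | 77.9% | 67.5% | 65.0% | 23 |
| VEGF | 27 | 90% | 90.5% | 84.1% | 82.7% | 33 |

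The one-sided column is within about 1 point of the plan in every row. The two-sided column is lower than the plan in every row, by 5.7 to 12.6 points. Using t critical values takes off a further 1.4 to 2.5 points.

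**Could a different correlation explain it?** For a two-sided slope test to give the stated powers, ρ would have to lie between 0.665 and 0.701, with a different value for each row. The plan states 0.60. Its cited default of 0.65 gives 81.8, 88.7, 63.1, 67.7, 73.3 and 88.5%, which still falls short throughout.

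**The .73 in the sub-group paragraph.** A partial eta-square of .0291 gives f² = .0291/.9709 = 0.02997. With 40 patients, 3 visits and ρ = 0.60, the noncentrality is 40 × 3 × 0.02997/0.40 = 8.99, and a 2-df interaction F test at 0.05 has power 0.753. The 20% effect, however, has noncentrality z² = 2.263² = 5.12, which corresponds to an eta-square of about 0.017. Power is then about 0.61 (1 df) or 0.50 (2 df). At 20 per group, a noncentrality of 8.99 matches a linear slope difference of √8.99 × 0.3536 = 1.06 per week, not 0.8.

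**The case against.** Four points can be made for the plan.

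1. **One-sidedness is inferred, not documented.** This is true. The normal approximation also rounds to 85, 91 and 69 where the plan prints 84, 90 and 70. But two outcomes, three slope differences and four sample sizes all fit the one-sided value closely, and none fits the two-sided value.

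2. **Another two-sided method comes near.** A week-12 analysis of covariance with the same SD and correlation gives 85.1, 91.3, 67.0, 71.6, 77.0 and 91.1%. It misses the 70% by 3 points, and it is neither the method named in the sample-size text nor the planned analysis. The finding should therefore be read as applying under the named slope method.

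3. **The sub-group paragraph reaches about 73% with a non-directional F test.** It does, but that paragraph derives its effect size from the .73, and the size it states is larger than the 20% effect to which the 73% belongs. It does not support the figure independently.

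4. **The hypothesis is directional, and this is a pilot for which the plan calls accurate power calculation infeasible.** A directional hypothesis does not make the test one-sided, and the analysis text asks only whether slopes differ. The pilot label excuses uncertain inputs. It does not excuse six published powers, used to call 18 per group sufficient, that do not match the planned test.

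One caution stands. The two-sided figures are themselves conditional on a simpler model than Data Analysis allows.

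**Conclusion.** The concern holds. Under the plan's own method and inputs, the six powers in Sample Size Estimation are those of a one-sided 5% test, while the planned interaction test is two-sided in form. The headline 73% is about 62% (about 60% with t critical values), and the 84% is about 76.5% (about 74%). The smallest gaps, at the two 90% figures, are about 6 points. The largest, at the 70% figure, is about 13.

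This rests on reading the p<0.05 threshold as two-sided, which the analysis text supports and nothing contradicts. It also assumes linear time with a single interaction term, a common SD and correlation, no random slope, and n completers per group with full data. Categorical time, a random slope or losses below the stated n would change the figures, and losses would lower them. The enrolment target and the analysis are not in question here; the stated power is.

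**What to change.** State that the 0.05 level is two-sided in the Synopsis (Statistics), in Sample Size Estimation and in Data Analysis. Then restate the figures:

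- CD34+/KDR+, 25% effect: 76.5% at 18 and 84% at 22 per group.
- CD34+/KDR+, 20% effect: 57% at 18 and 62% at 20 per group.
- VEGF: 68% at 18 and 84% at 27 per group.
- Table: replace the four power entries to match.
- Synopsis: replace 73% with 62%, and say that this is for the 20% effect with 20 completers per group.
- Sub-Group Subject Number Breakdown: replace .73 and re-derive the eta-square and the three-group total of 51 that rest on it.

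Add one sentence giving the conditions: linear slopes, correlation 0.60, complete data, normal approximation, with t critical values taking off a further 1.4 to 2.5 points. Revise the sentence that calls 18 per group sufficient so that it reflects the lower power.

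The cost is wording only. No patients, visits or analyses are added, but the stated power is less favourable.

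### The sub-group section borrows the linagliptin v placebo effect size to justify comparisons between non-randomised background-therapy groups, and leaves the meaning of GROUP unsettled

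*Combined protocol and SAP*

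**What the plan says.** The Sub-Group Subject Number Breakdown in section 5 opens with the trial's own question: "To estimate the effect of linagliptin on CD34+/KDR+ cells". It recalls that "we originally proposed a sample size of 20 per group in 2 groups, giving us power = .73". The conditions given for that figure are "assuming alpha=.05, between time points of .60 and equal allocation between groups", and the interaction being modelled is expressed as "partial eta-square = .0291". It then changes the groups: "Using 3 groups (Insulin only, metformin only, metformin + insulin), with the same effect size, we would achieve this same level of power", with 51 patients in total, 17 per group. Because few candidates take insulin, it keeps the total at 40 and enrols 22 on metformin only, 12 on both and 6 on insulin only. Its remarks on power concern background therapies alone. One is a concession: "We recognize that we will be underpowered for comparisons between the Metformin + insulin versus Insulin groups". The other describes power against the metformin-only group as still reasonable. The section mentions neither placebo nor a split by arm within 22/12/6.

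Data Analysis, also in section 5, says that if the global interaction test is significant, "subsequent significance testing of the pairwise comparisons of group slopes group will be adjusted for multiple comparisons". The model printed there has one Group coefficient and one Time x Group coefficient. If time is categorical, the text allows two indicators for the GROUP by TIME interaction.

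Elsewhere the comparison is linagliptin v placebo, 20 v 20: the Study Schema in the synopsis, and Patient Definition and Selection and Study Design Overview under section 4.5. Section 4.2 specifies permuted blocks and mentions no stratification by background therapy.

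**The concern.** The effect size was derived for a randomised drug contrast. The three groups are defined by what patients already take, which is not randomised, and roughly half of each group receives placebo. Nothing links the size of a drug effect to the difference in slope between insulin users and metformin users. That difference is confounded with disease duration, severity and whatever else led to the prescription.

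The matter reaches the analysis through the word group. Two arms form a single pair, so a step of adjusted pairwise comparisons implies three or more groups, and the sub-group section supplies the only such grouping in the documents. An analyst who follows both sections together could run a three-level test and report a confounded background difference as a linagliptin finding.

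**Working it through.** **Inputs.** SD 15, correlation 0.60, weeks 0, 6 and 12, and a 20% effect on 4 cells/week, that is 0.8 cells/week (section 5, Sample Size Estimation). Partial eta-square 0.0291 and 22/12/6 (sub-group section). Alpha is 0.05 ("A p-value of less than 0.05 will be considered statistically significant", synopsis, Statistics); sidedness is not stated. All figures assume complete data on 40 patients.

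**1. The plan's 51.** Repeated-measures interaction, noncentral F with k groups and m = 3 visits: f² = 0.0291/0.9709 = 0.0300; λ = f²·N·m/(1 − 0.60); df = (k−1)(m−1) and (N−k)(m−1).

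| k | N | λ | Power |
|---|---|---|---|
| 2 | 40 | 8.99 | 0.753 |
| 3 | 48 | 10.79 | 0.728 |
| 3 | 51 | 11.46 | 0.758 |
| 3 | 40 | 8.99 | 0.631 |

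So 51 is the smallest balanced three-group total that reaches 0.73. A six-cell test of arm x background x time gives almost the same power at 51 (0.757), so the total alone does not identify the test. But 17 per group cannot be split 1:1 by arm, and a balanced six-cell layout needs a multiple of 6 (48 gives 0.726, 54 gives 0.785). The stated layout fits three groups without an arm factor. At the retained total of 40, even with equal groups, the borrowed effect size gives 0.63.

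**2. The plan's 0.73.** SD of a patient's slope = 15·√(0.40/72) = 1.118 cells/week. For 20 v 20 and 0.8 cells/week, SE = 1.118·√(2/20) = 0.354. The normal approximation gives 0.732 one-sided and 0.619 two-sided. The stated figure therefore belongs to the linagliptin v control slope contrast, and matches a one-sided 5% test.

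**3. What a three-group test with arm ignored can see.** Simulation, 20,000 trials per scenario, 22/12/6, no background difference, same drug effect in every background group:

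| Drug effect, cells/week | Three-group test, arms not balanced within background | Arms balanced within background | Two-arm slope test, two-sided |
|---|---|---|---|
| 0.8 | 5.0–5.1% | 3.6–3.9% | 59–60% |
| 1.0 | 4.8–4.9% | 2.8–3.2% | 79% |

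The ranges cover a slope F test and a repeated-measures ANOVA. If only metformin-only patients respond (0.8 cells/week), the three-group test rejects in 11–13%.

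**4. The same test when the drug does nothing.** Let both insulin groups (12 + 6 = 18) differ in slope from metformin-only (22) by d. Then λ = (22·18/40)·d²/1.118² = 7.92·d², with 2 and 37 df:

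| d, cells/week (assumed) | λ | Probability of p < 0.05 |
|---|---|---|
| 0.25 | 0.50 | 0.086 |
| 0.5 | 1.98 | 0.209 |
| 0.8 | 5.07 | 0.476 |
| 1.0 | 7.92 | 0.675 |

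With repeated-measures ANOVA in place of the slope test, simulation gives 0.37 at 0.8 and 0.57 at 1.0. If only the insulin-only group differs, by 1.0, the slope test gives 0.39.

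**5. Power against metformin-only.** Take 0.8 cells/week as the background difference, only because the plan carries the effect size over. SE = 1.118·√(1/n₁ + 1/n₂), noncentral t:

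| Comparison | SE | Two-sided | One-sided |
|---|---|---|---|
| 22 v 12 | 0.401 | 0.49 | 0.62 |
| 22 v 6 | 0.515 | 0.32 | 0.45 |

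The multiplicity adjustment lowers these: a Bonferroni correction for three pairs gives about 0.35 and 0.20, two-sided, normal approximation.

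**6. The randomised contrast within background groups.** At best 11 v 11, 6 v 6 and 3 v 3. SD of the week 12 minus week 0 change = 15·√0.8 = 13.4 cells. The 95% CI half-width is t·13.4·√(2/n): 2.09·5.72 = 12, 2.23·7.75 = 17 and 2.78·10.95 = 30 cells.

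**7. GROUP in the model.** With three visits, a two-level GROUP needs (2−1)(3−1) = 2 interaction indicators and a three-level GROUP needs 4. The text specifies two, which fits arms only. The pairwise step fits three or more groups only.

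**The case against.** The strongest reply is that the linagliptin question has not been displaced. The 20 v 20 comparison stands in the synopsis, in section 4.5 and in the sample-size text. Data Analysis checks study groups for imbalance after randomisation, prints a model with one Group coefficient, and uses two interaction indicators. A global interaction test is also natural with two arms when time is categorical. The total of 51 was never adopted, and 22/12/6 can be read as recruitment quotas drawn from the candidate pool. The trial is called a pilot, and one comparison is conceded to be underpowered.

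Most of this stands. A reader might infer that the plan replaces the arm comparison with a background comparison, or that it pools the arms. Neither is written: pooling is only inferred from how 51 was calculated. A reader might also infer that a three-group test has no power at all for linagliptin; that is exact only for an effect common to all background groups. The false-finding rates in step 4 need a background slope difference that the documents do not give, so no single value should be quoted as the risk.

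What the reply does not rescue is the transfer of the effect size, the description of power as reasonable, or the pairwise step, which is empty if GROUP means arm and misleading if it means background therapy.

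**Conclusion.** The concern holds within limits and should be fixed. The sub-group section sizes and justifies comparisons of non-randomised groups with an effect size that belongs to the randomised arms, and those comparisons do not answer the linagliptin question. The claim of reasonable power is not met on the plan's own SD, correlation and 20% effect, on either a one-sided or a two-sided test. GROUP carries two competing meanings across the sub-group section and Data Analysis. The primary two-arm model is not itself invalidated. The results rest on complete data, compound symmetry at 0.60 and, for the inert-drug scenarios, assumed background differences of 0.25 to 1.0 cells/week.

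**What to change.** In section 5, state in both the sub-group section and Data Analysis that GROUP is the randomised arm, linagliptin v placebo. Delete the argument for 51 patients at 17 per group, the sentence claiming reasonable power, and the pairwise step. Keep 22/12/6 as recruitment quotas only.

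If background therapy is to be examined, report the linagliptin-placebo difference with a 95% CI within each background group, or fit one arm x time x background term. Label it exploratory and say that it is imprecise: half-widths of about 12, 17 and 30 cells at best, since section 4.2 mentions no stratification that would balance the arms within background groups. For metformin-only v insulin-containing patients, the SE of the difference in drug effect is 13.4·√(2/11 + 2/9) = 8.5 cells, so 80% power needs about 25 cells, twice the 12-cell effect in the plan's table.

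The cost is wording, settled before unblinding, with no extra patients or data. The sponsor gives up a claim about background therapies that the design cannot support.
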